5.5.2.2 Discontinuations as Events for Brexpiprazole Group

The second sensitivity analysis will be conducted by considering 20% randomly selected discontinued subjects (other than subjects discontinued because of study termination by the sponsor) in Phase C on Brexpiprazole treatment without meeting the relapse criteria as having the relapse at one day after the discontinuation date. Then the Cox Proportional Hazard model with treatment as the fixed effect will be generated.

For relapsed subjects in Phase C, time to event will be calculated as the date of meeting criteria - randomized date + 1. For the 20% selected discontinued subjects in the brexpiprazole treatment group without meeting the relapse criteria in Phase C, time to event will be calculated as the date of discontinuation - randomized date + 2. For the other 80% discontinued subjects on brexpiprazole treatment group without meeting relapse criteria in Phase C and all discontinued subjects on placebo treatment group without meeting relapse criteria in Phase C, they will be considered as censored observations at the discontinuation date. Time to censoring will be calculated as the date of discontinuation - randomized date + 1. Subjects who complete the double-blind treatment period of 6 months in Phase C will be considered as censoring observations. Time to censoring will be calculated as completion date - randomization date + 1. In total, 30 imputations will be made for this sensitivity analysis. Again, SAS PROC MIANALYZE will be used to combine the results of these 30 imputations to provide a final result.

5.5.3 Effect of COVID-19 on the Primary Endpoint

In earlier 2020, an outbreak of respiratory disease caused by a novel coronavirus named “Coronavirus Disease 2019” (COVID-19) had widely spread all over the world. On March 13, 2020, the President of the United States declared a national emergency in response to COVID-19. It is after this date, centers enrolled in this study had implemented remote visits in response to this pandemic. In order to assess the effects of this change on the primary efficacy endpoint, subgroup analysis is planned to assess the effect of COVID-19 on the primary analysis.

The COVID subgroup is defined for subjects enrolled in Phase C and classified according to the following criteria: all subjects randomized into Phase C after March 13th will start the remote access or remote changes for their visits and will be classified as COVID=Yes; subjects randomized on or before March 13th 2020 will have COVID=No. The COVID-19 related changes will include but not limit to remote visit, missed visit (especially for efficacy assessments), missed assessment, discontinuation due to COVID-19.

A Cox Proportional Hazard model with treatment as the fixed effect will be fitted by each of the two COVID subgroups. Subjects who are randomized on or before March 13th, 2020 will be censoring on March 13th 2020 or the last in-person visit whichever is first. This way the analysis for the COVID=No subgroup will estimate the hazard ratio of the two treatment groups without any impact from the COVID. The within subgroup p-value from the log-rank test from the treatment comparison will be provided for each subgroup, together with the hazard ratios and their 95% confidence intervals using the Cox Proportional Hazard model with treatment as a fixed effect in the model. A listing of all participants affected by the COVID-19 related study disruption/changes will be presented with a description of how the individual's participation was altered.

5.5.4 Secondary Efficacy Analysis

5.5.4.1 Secondary Efficacy Analysis

The secondary efficacy endpoints evaluated for Phase C will include:

- Time-to-Functional relapse
- Proportion of subjects meeting relapse criteria
- Proportion of subjects maintaining remission
- Change from baseline to endpoint in MADRS total score (LOCF)
- Change from baseline to endpoint in CGI-S score (LOCF)
- CGI-I score (LOCF)

- Change from baseline in SDS mean total score and each of the SDS individual item scores (LOCF)

5.5.4.2 Analysis of Functional Relapse

The secondary efficacy endpoint is time-to-functional relapse based on a 30% increase in Sheehan Disability Scale (SDS) mean total score from Phase C baseline and at least one SDS sub-score at 4 or greater and a SDS total score great than or equal to 7 when all 3 sub-scores are available (or SDS total score greater than or equal to 5 when work/school item does not apply) at Phase C visits. In the event that the SDS phase C baseline is 0, the evaluation will be based on the total SDS and SDS sub-score criteria at Phase C. Time to functional relapse will be the first SDS assessment in Phase C that met the functional relapse criteria.

The Sheehan Disability Scale (SDS) is a self-rated instrument used to measure the effect of the patient's symptoms on work/school, social life, and family/home responsibilities. For each of the three items, scores range from 0 through 10. The number most representative of how much each area was disrupted by symptoms is marked along the line from 0 = not at all, to 10 = extremely. For the work/school item, no response will be entered if the patient did not work or go to school for reasons unrelated to the disorder and a response therefore not being applicable. The Mean total SDS Score will be calculated over the three item scores. All three item scores need to be available with the exception of the work/school item score when this item is not applicable. In the event that work/school item does not apply, the other two items will be averaged as the mean total score.

Event/censor time will be defined as the following: if subjects meet the relapse criteria for functional relapse, the SDS assessment date during Phase C will be used as an event date; If the subject withdraw or discontinue study without meeting the functional relapse criteria, the withdraw/discontinuation date will be the censoring date. For completed subjects, they are considered as censoring at the completion, i.e., time to censor = completion date - randomized date + 1. If time to event/censor is great than 196 days, this subject no matter if he/she discontinued or completed for Phase C will be considered as censoring at Day 196. At interim analysis, the interim analysis cut-off date will be used as the censor date. Log-rank test will be used for the time-to-functional relapse comparisons similar to the primary efficacy analysis.

5.5.4.3 Analysis of Other Secondary Efficacy Endpoints for Phase C

Baseline for Phase C is defined as the last visit of Phase B prior to the first dose of double-blind trial medication in Phase C. Analysis of the change from baseline for other secondary efficacy endpoints will be based on subjects in the Phase C Efficacy Sample. Analysis of the CGI-S score endpoint will be based on subjects in the Phase C Efficacy Sample who have post-baseline CGI-S observations. The analysis will be based on all subjects who have been randomized and taken one dose of IMP in Phase C.

The proportion of subjects meeting relapse criteria as defined in Primary Efficacy Endpoint Section 5.5.1.1 will be analyzed by treatment group, visit (OC) and the subject's last visit (LOCF) in Phase C using the Chi-square test.

Subjects maintaining remission is defined as MADRS total score ≤ 10 . Analysis will be done at each visit (OC) and the final visit (LOCF) using Chis-square test.

The MADRS, CGI-S score and individual SDS score at endpoint will be analyzed at the last visit (LOCF) using an ANCOVA model. As an exploratory analysis, change from baseline variables including MADRS, CGI-S, and SDS will be analyzed by a Mixed Model Repeated Measures (MMRM) approach using observed data, with terms of treatment, trial center, visit, treatment-by-visit interaction, baseline and baseline-by-visit interaction. To avoid too many parameters in the statistical model, variance-covariance matrix with heterogeneous compound symmetry structure is assumed in the MMRM analysis. In addition, the count and frequency of SDS with work/school item not applicable at baseline will be summarized.

The CGI-I score at endpoint will be analyzed at the last visit of LOCF data using the Cochran-Mantel-Haenszel method based on raw mean score statistics.

Kaplan-Meier curves will be plotted for time to discontinuation due to all causes and the log-rank test will be used to test the differences in the survival curves.

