3.7.1.4 Double-blind Randomized Withdrawal Phase (Week 21 through Week 46/End of Phase C/Relapse) (Phase C)

The following assessments will occur during the Double-blind Randomized Withdrawal Phase:

- A qualified and certified rater will administer the MADRS *at Weeks 21 through 46*.
- The investigator (or qualified designee) will administer the CGI-S *at Weeks 21 through 46*.
- The subject will complete the SDS *at Weeks 21 through 46*.
- For subjects who discontinue early, attempts should be made to complete ALL evaluations, particularly efficacy assessments (ie, MADRS, CGI-S, and SDS), for the *Week 46/ET* visit prior to the administration of any new antidepressant medications. However, if the subject receives a new antidepressant prior to ET procedures, no efficacy assessments should be done.
- A complete physical examination (including waist circumference) will be performed *at Week 46 only*.
- Vital sign measurements (body weight, body temperature, blood pressure, and heart rate) will be recorded *at Weeks 21 through 46*. Blood pressure and heart rate are to be measured in the following order: supine, sitting, and standing after the subject has been in each position at least 3 minutes. Vital signs are to be completed before any blood is drawn.
- A standard 12-lead ECG will be performed after the subject has been supine and at rest for at least 5 minutes *at Weeks 29 and 46*. The ECG is to be completed before any blood sample is collected.
- A fasting blood draw should be collected for clinical laboratory tests (hematology and serum chemistry) and urine will be collected for urinalysis *at Week 46*. If fasting blood samples are not feasible, nonfasting blood samples may be collected. The laboratory tests will also include prolactin *at Week 46*. Vital sign and ECG assessments should be completed before any blood samples are collected.
- Blood alcohol will be tested *at Week 46*.
- Blood samples will be drawn for PK analysis *at Weeks 37 and 46*.
- A urine drug screen will be performed *at Weeks 33 and 46*.
- A urinary pregnancy test (WOCBP only) will be performed *at Weeks 33 and 46*. Any positive result must be confirmed by a serum pregnancy test. WOCBP with a positive serum pregnancy test result must discontinue the IMP and be withdrawn from the trial.

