3.3 Single-blind Stabilization (Phase B)

The following subjects will enter Phase B and receive single-blind brexpiprazole + open-label ADT for 12 weeks:

- Subjects who successfully complete Phase A
- Subjects who meet response criteria at the end of Phase A.

During Phase B, investigators will attempt to stabilize subjects on single-blind brexpiprazole for 12 weeks. Visits will occur weekly for; subjects will be assessed for stability at scheduled visits using the following criteria:

- Subjects must show $\geq 50\%$ improvement on the MADRS total score from Phase A baseline and a CGI-S score ≤ 3 for 12 consecutive weeks.
- The dose of brexpiprazole + ADT must be stable for at least the last 4 weeks of Phase B.

Subjects are allowed a maximum of 3 excursions from meeting the stabilization criteria during the 12-week period, as long as the excursions do not occur on 3 consecutive visits or on the last visit of Phase B.

Subjects not meeting stability criteria will be discontinued from the trial.

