5.5 Efficacy Analysis

5.5.1 Primary Efficacy Analysis

5.5.1.1 Primary Efficacy Endpoint

The primary efficacy endpoint of this trial is time-to-relapse by any criteria as defined in the blinded addendum to this protocol, measured from Week 20 (randomization) to the Double-blind, Randomized Withdrawal Treatment Phase).

Time-to-relapse (primary efficacy endpoint) is defined as meeting any of the following criteria (blinded to investigators) measured from randomization into Phase C:

- I. At the same visit, an increase on the MADRS total score of 50% from randomization and CGI-S score ≥ 4 , **OR**

- II. Hospitalization for depression, **OR**
- III. Discontinuation for lack of efficacy or worsening of depression, **OR**
- IV. Active suicidality, defined as a score of ≥ 4 on the MADRS item 10 **OR** an answer of “yes” on question 4 or 5 on the C-SSRS **OR** an answer of yes to any of the questions on the Suicidal Behavior section of the C-SSRS.

The time origin for measuring this event time is the date of randomization into the double-blind, placebo-controlled treatment phase (Phase C). Phase C Efficacy Sample is used in the primary analysis of the primary efficacy endpoint. The primary objective of statistical analysis is to compare the efficacy of brexpiprazole (2 to 3 mg/day) + ADT with that of placebo + ADT with regard to time-to-relapse. This will be achieved by testing the equality of the two survival curves by the log-rank test.

Interim analyses are planned to be performed at approximately 50% and 75% of events accrual time points using the O’Brian-Fleming boundaries for rejection of the null hypothesis. Details of the interim analyses are provided in the interim analysis plan.

A group sequential testing procedure will be employed with two planned interim analyses at approximately 50% (52 events) and 75% (78 events) events accrual time points, and a final analysis using 100% (approx. 104 events) events. The O’Brian-Fleming boundaries will be utilized in this analysis for the rejection of the null hypothesis to maintain an overall nominal significance level of 0.05 (two-sided). [REDACTED]

[REDACTED]

[REDACTED]

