5.5.1.2 Technical Computational Details for Primary Efficacy Analysis

Subjects who meet relapse criteria are considered as an event of relapse. For relapsed subjects in Phase C, time to event is calculated as the earliest date of time-to-relapse, defined as the time meeting relapse criteria - randomized date + 1. Below are the criteria to determine the relapse time for each relapse criteria:

- 1). If subjects meet the relapse criteria per MADRS and CGI-S assessments of criteria I, which are conducted on different dates, the later assessment date will be used as the relapse event date.
- 2). If subjects meet the relapse criteria per criteria IV, C-SSRS or MADRS, the earliest date of the evaluation that the criteria are met will be used as the relapse event date.
- 3). If subjects meet the relapse criteria per hospitalization due to worsening of depression and are reported as an adverse event (AE), the AE start date will be used as the relapse event date.
- 4). If subjects meet the relapse criteria per lack of efficacy or worsening of depression but are not reported as an AE, the first two criteria stated prior will be checked. The earliest date that criteria 1) or 2) is met will be the relapse event date. If none of the above is applicable, then the discontinuation date will be the relapse date.

Subjects who complete the double-blind treatment period of 26 weeks or discontinue treatment without meeting the relapse criteria (including those who are lost to follow-up during treatment period) in Phase C will be considered as censored observations as

mentioned above. For the withdrawn (rather than lack of efficacy) subjects in Phase C, they are considered as censoring at discontinuation, i.e., time to censor = discontinuation date - randomization date + 1. For the completed subjects, they are considered as censoring at the completion, i.e., time to censor = completion date - randomized date + 1. If the time to event/censor is great than 196 days, the subject, no matter discontinued or completed Phase C, will be considered as censoring at Day 196.

The log-rank test will be used to test the equality of the two survival curves.

Additionally, a nominal 95% confidence interval for the hazard ratio (brexpiprazole vs. placebo) will be provided using the Cox Proportional Hazard model with terms for treatment in the model. Ties in the event times will be handled by using the exact option in SAS PROC PHREG.

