5.5.4.3.2 Technical Computational Details for Other Secondary Efficacy Analysis

- 1) In general, data for MADRS, CGI-S, and SDS assessment after the relapsed dates for the relapsed randomized subjects will not be included in the Phase C efficacy summary tables.
- 2) Time to discontinuations due to all causes rather than the sponsor discontinued trial will be measured from the date of randomization to date of early termination for withdrawn subjects in Phase C, i.e., time to discontinuation = discontinuation date - randomization date +1. Subjects discontinuing the trial due to the sponsor discontinued trial in Phase C will yield censoring observations for time to discontinuation and be considered censoring at discontinuation, i.e., time to censor= discontinuation date - randomization date +1. Subjects completing the entire treatment duration of Phase C will yield censoring observations for time to discontinuation and be considered censoring at completion, i.e., time to censor= completion date - randomization date +1. If time to discontinuation/completion is great than 196 days, the subject will be considered as censoring at Day 196, no matter if he/she discontinued or completed Phase C.

Time to discontinuation due to all causes rather than the sponsor discontinued trial in Phase B will be calculated for Phase B efficacy sample using the similar method. Time to discontinuations due to all causes rather than the sponsor discontinued trial in Phase B will be measured from the 1st dosing date of Phase B to date of early termination for withdrawn subjects in Phase B, i.e., time to discontinuation in Phase B = discontinuation date - 1st IMP dosing date of Phase B +1. Subjects discontinuing the trial due to the sponsor discontinued trial in Phase B will yield censoring observations for time to discontinuation and be considered censoring at discontinuation, i.e., time to censor= discontinuation date - 1st IMP dosing date of Phase B +1. Subjects continuing into Phase C will yield censoring observations at randomization date, i.e., time to censor in Phase B = randomization date - 1st IMP dosing date of Phase B +1. If time to discontinuation/censor is great than 98 days, this subject will be considered as censoring at day 98 no matter if she/he is randomized into Phase C.

- 3) Computing of Scale Scores
 - a) The CGI-S and CGI-I of 0 will be set to missing because value means ‘not assessed’.

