5.5.6 Exploratory Efficacy Analysis

The number and percentage of subjects meeting the below the specified criteria are summarized by visit:

- Subjects responding to treatment during Phase A by visit as specified in Section 3.2.
- Subjects meeting stabilization criteria of MADRS and CGI-S at any point during Phase B Section 3.3.
- Subjects achieving remission at any time point during Phase B.

Subjects achieving remission in Phase B is defined as a MADRS total score ≤ 10.

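### 'Maintaining remission' in Phase C is defined by MADRS 10 or less alone, so it can include subjects not in remission at randomisation and some who have relapsed

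*SAP*

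**What the plan says.** The percentage of subjects maintaining remission is listed among the other secondary endpoints in Protocol 3.5.2 and 7.4.2.2 and again in SAP 5.5.4.1. Protocol 7.4.2.2 says only that remission rests on MADRS criteria. SAP 5.5.4.3 supplies the rule: "Subjects maintaining remission is defined as MADRS total score ≤ 10". The analysis is by visit (OC) and at the final visit (LOCF), in all subjects randomised and dosed in Phase C. SAP 5.5.6 uses the same threshold for a different idea: "Subjects achieving remission in Phase B is defined as a MADRS total score ≤ 10".

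Four other rules bear on who is counted.

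- **Entry to Phase C (SAP 3.3).** Subjects need at least 50% "improvement on the MADRS total score from Phase A baseline and a CGI-S score ≤ 3 for 12 consecutive weeks". A limited number of excursions is allowed, but none at the last Phase B visit. There is no absolute MADRS limit.
- **Relapse (SAP 5.5.1.1).** Criterion I is "an increase on the MADRS total score of 50% from randomization and CGI-S score ≥ 4" at the same visit. Criteria II to IV are hospitalisation for depression, discontinuation for lack of efficacy or worsening, and active suicidality. None of these three uses the MADRS total.
- **Dating of relapse (SAP 5.5.1.2).** When the two criterion I ratings fall on different days, "the later assessment date will be used as the relapse event date". For hospitalisation reported as an adverse event, "the AE start date will be used as the relapse event date".
- **Ratings after relapse (SAP 5.5.4.3.2).** In general, MADRS, CGI-S and SDS "assessment after the relapsed dates for the relapsed randomized subjects will not be included in the Phase C efficacy summary tables".

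Protocol 3.7.1.4 asks sites to try to complete every exit evaluation before a new antidepressant is given, but "if the subject receives a new antidepressant prior to ET procedures, no efficacy assessments should be done".

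**The concern.** To maintain remission, a subject has to be in remission at the start and not lose it. The SAP rule tests neither. It measures whether a MADRS score is at or below 10 at a given visit, which is a different quantity from the one the endpoint's name promises.

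Two groups can be counted who should not be. The first is subjects randomised above 10 who fall to 10 or below later; they have newly remitted. The second is subjects who met a relapse criterion but whose last retained MADRS is 10 or less. In a randomised withdrawal trial, the second group would be failures on the primary endpoint and successes on this one. At stake are the meaning of a named secondary endpoint and, to a small degree, the size of its last-visit treatment difference.

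**Working it through.** The plan states no figure for remission, so there is none to reproduce. The check uses threshold arithmetic and the planned relapse rates.

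**1. Can a subject enter Phase C above 10?** An improvement of at least 50% allows a randomisation score of up to half the Phase A baseline. For whole-number scores:

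| Phase A MADRS | Highest score allowed at randomisation |
|---|---|
| 21 | 10 |
| 22 | 11 |
| 26 | 13 |
| 30 | 15 |
| 40 | 20 |

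So yes, from a Phase A score of 22. The entry severity rule is on the HAM-D17, so the MADRS at entry is not bounded. The documents do not allow an estimate of how many subjects this concerns.

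An illustration with assumed rates: 80% of baseline remitters are at 10 or below later, and 20% to 40% of the others reach it. If 50% are in remission at randomisation, the SAP rule gives 0.5×0.8 + 0.5×0.2 = 50% up to 0.5×0.8 + 0.5×0.4 = 60%, while 0.5×0.8 = 40% of all subjects started in remission and are still there. If 90% are in remission at randomisation, the figures are 74% to 76% against 72%. This is a gap in labelling within each arm, not a difference between arms.

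**2. Can a relapser have a last MADRS of 10 or less?** There are three routes.

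- Criterion I: the score must reach 1.5 times the Phase C baseline. 1.5×6 = 9, but 1.5×7 = 10.5. Baselines of 1 to 6 therefore allow it, if the CGI-S is 4 or more.
- Criteria II to IV: the MADRS total is not part of the criterion.
- A pre-relapse score carried by LOCF: mainly a hospitalisation dated at the adverse-event start, with later ratings excluded, or an exit rating not done because a new antidepressant came first. Visits are four weeks apart from Week 25 to Week 45, so the carried score may be weeks old.

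**3. How often?** The dating rules limit the third route. Criterion I and IV relapses are dated at the assessment. Lack-of-efficacy or worsening relapses not reported as adverse events are dated at the qualifying assessment or, failing that, at discontinuation. A rating made by that date is kept.

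**4. Effect on the last-visit difference.** Inputs: relapse of 30% on placebo and 16% on brexpiprazole (SAP 4). These agree with the plan's hazard ratio: ln(0.84)/ln(0.70) = 0.49. Let q be the share of non-relapsers, and r the share of relapsers, whose last MADRS is 10 or less, with subscripts P and B for the arms. Assume every relapser has a Phase C score.

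- SAP rule: (0.84 q_B + 0.16 r_B) − (0.70 q_P + 0.30 r_P)
- Relapse counted as failure: 0.84 q_B − 0.70 q_P
- Reduction under the SAP rule: 0.30 r_P − 0.16 r_B

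The q terms cancel whether or not they are equal.

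| r_P | r_B | Reduction, percentage points |
|---|---|---|
| 5% | 5% | 1.5 − 0.8 = 0.7 |
| 10% | 10% | 3.0 − 1.6 = 1.4 |
| 5% | 10% | 1.5 − 1.6 = −0.1 |

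With equal r the reduction is 0.14r. It changes sign when r_B/r_P exceeds 0.30/0.16 = 1.875. All values of r are assumptions.

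**The case against.** The best defence is that the exclusion of ratings after the relapse date already deals with relapse. It does not: it removes data and never sets a relapsed subject to not in remission, so it can leave an earlier score of 10 or less as the final value.

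Other parts of the defence stand. The testing hierarchy in Protocol 7.4.2.1 stops at the two SDS endpoints, and this is not one of them. Relapse itself is captured by the primary analysis and by the proportion relapsing at the last visit. The dating rules keep the exit score for most types of relapse, and a MADRS of 10 or less alongside a CGI-S of moderately ill or worse is probably an uncommon pairing.

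A reader might infer more than the documents support:

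- That admitting non-remitters biases the comparison. Randomisation balances them in expectation.
- That the rule necessarily works against brexpiprazole. That needs r to be equal in the two arms, or not much higher on brexpiprazole.
- That many of the 104 planned relapsers would be miscounted. Nothing in the documents supports a large r.
- That the by-visit tables are defective because relapsers leave them. SAP 5.1.1 defines observed cases openly, and Protocol 7.3 assigns them to by-visit analyses. The tables need only a clear label.

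**Conclusion.** The point holds as a minor finding. The definition does not match the endpoint's name, and relapsed subjects can be counted as maintaining remission. The first fault is one of labelling. The second changes the last-visit difference by 0.30 r_P − 0.16 r_B. With r equal in both arms, that is a dilution of 0.7 points at an assumed 5% and 1.4 points at an assumed 10%, with a possible reversal if r on brexpiprazole is more than about 1.9 times r on placebo. The result rests on the planned relapse rates and on values of r that the documents do not give; the dating rules suggest that r is small. The primary result, the key secondary results and type I error control are unaffected.

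**What to change.** Amend SAP 5.5.4.3 as follows.

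- At the last visit, count every subject who has met a relapse criterion as not in remission, whatever MADRS score is retained or carried.
- Report *maintaining remission* among subjects with MADRS 10 or less at Phase C baseline. This subset is fixed before randomised treatment, so the comparison between arms remains a randomised one. State whether a score of 10 or less is required at every Phase C visit up to the time point, so that a subject who loses and regains remission is classified unambiguously.
- Keep the all-subject table, labelled *in remission (MADRS 10 or less)*.
- Keep the by-visit tables as observed cases, labelled as describing subjects still in the trial.

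This needs SAP wording and programming, and no new data. The cost is a smaller denominator for *maintaining remission*: if an assumed 50% to 90% are in remission at randomisation, about 112 to 202 of the planned 225 per arm (225×0.5 = 112.5; 225×0.9 = 202.5). The all-subject table keeps the full sample.

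As a separate matter, the chi-square test in SAP 5.5.4.3 and the country-adjusted CMH test for percentages in Protocol 7.4.2.2 should be reconciled.
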